3. STUDY DESIGN

This is a prospective observational cohort study in patients with osteosarcoma (OS). All newly diagnosed OS patients are eligible to take part. Consenting patients are recruited and followed up for at least two years.

The main aim of the study is to establish a platform which supports the recruitment of a consecutive cohort of newly diagnosed OS patients, whose clinical outcomes will be fully annotated and linked to their molecularly characterised biospecimens. The platform will support continuous collection, analysis and interrogation of data to generate hypothesis driven questions quickly for further evaluation. This project extends the Bone Cancer Research Trust tumour banking initiative with funding allocated to provide the infrastructure to optimise collection and storage of tissue samples in the five diagnostic and surgical bone tumour centres in England. It includes the development and validation of clinically relevant biomarkers to identify patients at high risk of relapse and patients suitable for therapeutic studies.

The study will be conducted in two stages. In **Stage 1**, we established the feasibility of patient recruitment and biospecimen collection. In **Stage 2**, correlation with response to chemotherapy and outcome will help develop prognostic biomarkers and provide an opportunity to identify patients for specific therapies. The study will continue these objectives and maintain a platform for development of additional studies and development of therapeutic studies based on the findings from our initial work.

3.1. Study Objectives

3.1.1. Stage 1: Completed

Determined the feasibility of recruiting patients to a national study with high quality clinical data and biospecimen collection to address clinical and biological questions in OS. Its specific research objectives and associated analyses are detailed in Appendix 4 below.

3.1.2. Stage 2

To enrol >350 patients (including those enrolled in Stage 1) and to use the data and samples collected to begin to address the questions listed below.

Following completion of Stage 1 the research objectives of Stage 2 have been amended and adjusted to take into account previous findings:

- Describe variations in management of patients with OS across treatment sites in the UK, including how decisions are reached for tumours being deemed inoperable and how patients contribute to the final decision on surgical operability in terms of what surgery is acceptable.
- Describe current indications for radiotherapy (RT) as part of local therapy
- Describe the impact of variation in management of patients with OS across treatment sites in the UK on patient outcome
- Assess whether tumour margin and response to chemotherapy predict local recurrence in OS
- Use FFPE samples be used to validate WGS findings, identify patients for specific therapies and aid development of novel therapeutic trials
- Use FFPE samples to perform transcriptional and proteomic spatial profiling of OS
- Develop a legacy resource of OS IO data and patient models to accelerate future collaborative research efforts
- Establish novel *in vitro* experimental models of OS (cell lines, organoids, explants) to be used to address biological questions regarding the mechanism of response to chemotherapy and immune-directed therapies
- Create an OS IO data atlas portal
- Assess whether circulating biomarkers can be used as prognostic markers and to predict burden of disease, response to therapy and outcome
- Collect PBMCs from 20 OS patients at UCLH
- · Set up an OS imaging repository with NCITA
- Use two methodologies of circulating tumour cell (CTC) detection to isolate and quantify CTCs in a subset of 50 patients undergoing neoadjuvant chemotherapy
- Describe associations between tumour heterogeneity and clonal evolution on chemotherapy response and patient outcome and determine if this can be used to stratify patients for therapy
- Determine if Germline DNA alterations can be confirmed in OS
- Collect WGS samples for the OS population
- Determine if there can be an accelerated target development through partnership with the immune oncology alliance and establishment of OS immune patient models
- Explore whether new candidate immunotherapy drug targets for OS can be discovered based on cellular and genomic analysis
- Assess the value of SAM for longitudinal assessment of patient quality of life and identify predictors of variance in patient reported outcomes (PROs)
- Describe the routes and times to diagnosis for patients with OS, and assess whether this has any impact on patient outcome

3.2. Study Activation

UCL CTC will ensure that all study documentation has been reviewed and approved by all relevant bodies and that the following have been obtained prior to activating the study:

- Health Research Authority (HRA) approval, including Research Ethics Committee approval
- Adoption into NIHR portfolio
- Adequate funding for central coordination
- Confirmation of sponsorship
- Adequate insurance provision

4. SELECTION OF SITES/SITE INVESTIGATORS

4.1. Site Selection

In this protocol study 'site' refers to the hospital where study related activities are conducted.

Sites must be able to comply with:

- Clinical care, follow up schedules and all requirements of the study protocol
- Data collection requirements, including adherence to electronic data capture timelines as per section 11.4
- Biological sample collection, processing and storage requirements
- Monitoring requirements, as outlined in protocol section 14 (Study Monitoring and Oversight)

4.1.1. Selection of Principal Investigator and other investigators at sites

Sites must appoint an appropriate Principal Investigator (PI), i.e. a health care professional authorised by the site to lead and coordinate the work of the study on behalf of the site. Coinvestigators must be trained and approved by the PI. All investigators must be medical doctors and have experience of treating osteosarcoma. The PI is responsible for the conduct of the study at their site and for ensuring that any amendments are implemented in a timely fashion. If a PI plans to take a leave of absence UCL CTC must be informed promptly. For absences greater than three months, or where the PI is no longer able to perform their duties at the site, a new suitable replacement PI must be identified by the site and UCL CTC notified.

UCL CTC may terminate recruitment at a site where a suitable replacement PI has not been identified within three months.

4.1.2. Training requirements for site staff

All site staff must be appropriately qualified by education, training and experience to perform the study related duties allocated to them, which must be recorded on the site delegation log.

CVs for all staff must be kept up to date, signed and dated and copies held in the Investigator Site File (ISF). A current, signed copy of the CV for the PI must be forwarded to UCL CTC upon request.

4.2. Site initiation and Activation

4.2.1. Site initiation

Before a site is activated, the UCL CTC trial team will arrange a site initiation with the site which the PI, and site research team must attend. The site will be trained in the day to day management of the study and essential documentation required for the study will be checked.

Site initiation will be performed for each site by telephone/video conference. Re-initiating sites may be required where there has been a significant delay between initiation and enrolling the first patient.

4.2.2. Required documentation

The following documentation must be submitted by the site to UCL CTC prior to a site being activated by the UCL CTC trial team:

- Site Registration Form (identifying relevant local staff)
- Relevant institutional approvals
- A completed site delegation log that is initialled and dated by the PI (with **all** tasks and responsibilities delegated appropriately)
- A signed and dated copy of the PI's current CV (with documented up to date GCP training, or copy of GCP training certificate)

In addition, the following agreement must be in place:

• A signed site agreement between the Sponsor and the relevant institution (usually an NHS Trust or Health Board)

4.2.3. Site activation

Once the UCL CTC trial team has received all required documentation and the site has been initiated, notification of site activation will be issued to the PI, at which point the site may start to approach patients.

Following site activation, the PI is responsible for ensuring:

- adherence to the most recent version of the protocol and Laboratory Manual which provides detailed instructions on biological sample collection, processing, storage and shipping
- all relevant site staff are trained in the protocol requirements
- appropriate recruitment and medical care of patients in the study
- timely completion of eCRFs (including assessment of all adverse reactions related to study procedures)
- prompt notification and assessment of all serious adverse reactions related to study procedures

5. INFORMED CONSENT

Sites are responsible for assessing a patient's capacity to give informed consent.

Sites must ensure that all patients have been given the appropriate current approved version of the patient information sheet(s), are fully informed about the study and have confirmed their willingness to take part in the study by signing the appropriate current approved consent form.

Sites must assess a patient's ability to understand verbal and written information in English and whether or not an independent interpreter or NHS approved translator would be required to ensure fully informed consent. If a patient requires an interpreter and none are available prior to consent, and for the duration of the potential participant's time on the study, the patient should not be considered for the study.

The PI, or, where delegated by the PI, other appropriately trained site staff, are required to provide a full explanation of the study to each patient prior to study entry. During these discussions, the current approved patient information sheet for the study should be discussed with the patient.

Patients should be given adequate time to consider and discuss participation in the study. However, patients may consent on the same day they are given the information sheet if this is more convenient for them. In such cases, a member of the research team at the hospital must phone the patient in the following days to confirm that they are still willing to participate in the study.

Written informed consent on the current approved versions of the consent forms for the study must be obtained before any study specific procedures are conducted. The discussion and consent process must be documented in the patient medical notes.

Site staff are responsible for:

- checking that the current approved versions of the patient information sheets and consent forms are used
- giving the patient a copy of the patient information sheet
- checking that information on the consent form is complete and legible
- checking that the patient has initialled all relevant sections of the consent form and signed and dated the form
- checking that an appropriate member of staff has countersigned and dated the consent form to confirm that they provided information to the patient giving the patient a copy of their signed consent form
- checking that an appropriate member of staff has made dated entries in the patient's medical notes relating to the informed consent process (i.e. information given, consent signed etc.)
- following registration, adding the patient's study number to all copies of the consent form, which should be filed in the patient's medical notes and investigator site file

The right of the patient to refuse to participate in the study without giving reasons must be respected. All patients are free to withdraw at any time. Also refer to section 15 (withdrawal of patients).

5.1. Additional information for patients under 16

The person with parental responsibility or legal guardianship of the child must be informed of all aspects of the study. The child must also be informed about the study to the extent compatible with their understanding. The same information must be provided to children of all ages, however the level of detail is age appropriate.

Information sheets are available for the following age groups:

- 06 09 years old
- 10 12 years old
- 13 − 15 years old

There is also an information sheet available for parents/legal guardians.

The patient and parent/legal guardian should be given adequate time to consider and discuss participation in the study. However, the patient and parent/legal guardian may consent on the same day they are given the information sheet if this is more convenient for them. In such cases, a member of the research team at the hospital must phone the patient and parent/legal guardian in the following days to confirm that they are still willing to participate in the study.

Written informed consent on the current approved version of the parent/legal guardian consent form for the study must be obtained before any study specific procedures are conducted. If capable the child may give assent by signing and personally dating the informed consent form, in addition to the parent or legal guardian. The discussion and consent process must be documented in the patient medical notes.

A child's refusal to participate in the study must be respected.

5.2. Additional information for adult patients lacking capacity to consent

Section 5.2 is NOT to be applied at any Scottish or Northern Irish ICONIC sites.

It is recognised that there are several genetic syndromes which cause both osteosarcoma and learning disabilities which may mean a patient does not have the capacity to consent. Where possible, these patients should be given the opportunity to participate in the study.

The person with duty of care for a patient lacking capacity must be informed of all aspects of the study. Where appropriate, the patient should also be informed about the study to the extent compatible with their understanding (for example one of the child patient information sheets could be used that is compatible with the patient's understanding).

The person with duty of care should be given the consultee information sheet. The person with duty of care, and the patient (where appropriate) should be given adequate time to consider and discuss participation in the study. However, confirmation of opinion that the patient would have no objection to taking part may be given on the same day as the information sheet if this is more convenient. In such cases, a member of the research team at the hospital must phone the person with duty of care in the following days to confirm that the patient is still willing to participate in the study.

Written confirmation of opinion that the patient would have no objection to taking part in the study will be collected on the current approved version of the consultee declaration form for the study, and must be obtained before any study specific procedures are conducted. If capable the patient may give assent by signing and personally dating the consultee declaration form, in addition to the person with duty of care. The discussion and process of confirming the patient would have no objection to taking part in the study must be documented in the patient notes.

A patient's refusal to participate in the study must be respected.

5.3. Remote consent

Appendix 1 gives guidance outlining the process for sites to follow if it is not possible for consent to be taken in person. All steps performed need to be documented clearly and filed in patient notes accordingly.

6. SELECTION OF PATIENTS

6.1. Screening Log

A screening log must be maintained and appropriately filed at site. Sites should record all patients identified with newly diagnosed osteosarcoma and the reasons why they were not registered in the study if this is the case. The log must be sent to UCL CTC when requested.

6.2. Patient Eligibility

Queries in relation to the eligibility criteria should be addressed prior to registration. Patients are eligible for the study if all the inclusion criteria are met and none of the exclusion criteria apply.

Patient eligibility must be confirmed by an investigator who is suitably qualified and who has been allocated this duty, as documented on the site staff delegation log, prior to registering the patient. Confirmation of eligibility must be documented in the patient medical notes and on the registration eCRF.

If a potentially eligible patient has a second primary OS, UCL CTC must be contacted before the patient is approached, so that eligibility for the study can be confirmed.

Patients must give written informed consent before any study specific investigations may be carried out. Refer to section 9.1 (Preregistration Assessments) for the list of assessments and procedures required to evaluate the suitability of patients prior to entry.

Patients who do not wish to complete the PROs but are willing to donate blood and/or tissue samples are eligible for the Study.

6.2.1. Inclusion criteria

 New histological diagnosis of osteosarcoma or in the absence of osteoid seen on biopsy, pathology and imaging supportive of a diagnosis of osteosarcoma.

(It is well recognised that some patients may present with features suggestive of osteosarcoma (under 40 years, radiological abnormality compatible) but in whom no osteoid is detected in needle biopsy. Although categorised as spindle cell tumour of bone, such patients are usually treated in an identical approach to osteosarcoma. A definite diagnosis of osteosarcoma is then often possible after surgery when the entire resection specimen is available.)

• Written informed consent of patient and/or parent/legal guardian or written confirmation of opinion of person with duty of care where applicable.

6.2.2. Exclusion criteria

• Diagnosis more than four months prior to registration

7. REGISTRATION PROCEDURES

Patient registration will be performed via a remote electronic data capture system (MACRO) hosted by UCL CTC. Please refer to the registration instructions provided in the ICONIC Database User Manual for sites. Patients must be confirmed to be eligible and have given consent prior to registration.

Site staff responsible for patient registration must request access to the eCRF database by completing the delegation log and their contact details on the site database user access form. Access to the database and instructions are provided by UCL CTC.

Note that patient initials, age at study entry, details of the Sarcoma MDT site and date of diagnosis are required to register a patient.

Upon registration confirmation from UCL CTC a study number will be assigned to the patient. This will be in the registration confirmation email which UCL CTC will send to the person registering the patient.

The study number must be recorded in the patient notes.

CONTACT DETAILS

ICONIC Trial Coordinator: [name]

ICONIC email: [contact]

ICONIC Remote Db Access: https://rde.ctc.ucl.ac.uk/

UCL CTC office hours: 09:00 to 17:00

Monday to Friday excluding Bank Holidays

(UK time)

Once a patient has been registered onto the study they must be provided with the following:

• A copy of their signed consent form and patient information sheet(s).

After registration into the trial, the patient's general practitioner (GP) should be informed of the patient's involvement in the trial by the site completing and sending the completed GP letter, GP early diagnosis form and information sheet.

8. STUDY TREATMENT

No treatments are specified by this protocol. Patients should be treated according to national guidelines including *UK guidelines for the management of bone sarcomas*²⁹ and applicable current and future NICE guidance.

9. STUDY ACTIVITIES

Please also see Schedule of Events tables in Appendix 2

9.1. Preregistration

The following is required to evaluate the suitability of patients for the study:

• Histological confirmation of osteosarcoma, including date

The following patient information is also required in order to register the patient:

- Age at time of registration
- Sex

9.2. Baseline

9.2.1. Baseline: Clinical Data

The following data should be collected from routine assessments carried out within 28 days of registration:

Medical History

- History of previous cancer
- Relevant previous medical conditions, procedures and treatments
- Current medical conditions, signs and symptoms
- Cancer signs and symptoms
- Duration of symptoms
- Causative risk factors (family history, previous radiotherapy, Paget's disease etc.)
- Smoking status

Baseline characteristics

- Physical examination (height and weight)
- Assessment of WHO performance status (patients ≥16) or Lansky performance status (see Appendix 3)
- Haematology: haemoglobin, ANC, lymphocytes, platelets
- Biochemistry: CRP, albumin, ALP, LDH, creatinine

Primary Tumour: Diagnostic imaging

- Date and type of scan and hospital where this was performed
- Site, size and location on bone of primary tumour
- Description of findings (intraarticular, pathological fracture, involvement of neurovascular bundle, presence of skip metastases etc.)

Primary tumour: Biopsy

- Date of biopsy and hospital where this was performed
- Tumour grade (assessed using TNM Classification for Osteogenic Sarcoma 15/01/2018) and histological subtype

Primary tumour: Surgery (if already performed)

- Date and type of surgery and hospital where this was performed
- Histological subtype
- Resection margins

Diagnostic staging: Imaging

- Date and type of imaging and hospital where this was performed
- Location, number and size of metastases, if applicable

Treatment plan

- Name and date of MDM where patient discussed
- Type of planned surgical operation or reason if surgery not to be performed (if known)
- Chemotherapy regimen, if planned or reason if no chemotherapy to be given
- Details on plans for radiotherapy or other care
- Adverse reactions: assessed only in relation to study procedures, e.g. venepuncture, biopsy for research when applicable.

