9.2.4. Baseline: Research Samples

(SEE SECTION 10 FOR SUMMARY)

All patients

- Whole blood sample for germline DNA (preferably collected at study entry, but may be collected at any point during the study)
- Whole blood sample for ctDNA, DNA methylation profiling/future research (optional)
 - NB if patient has started chemotherapy prior to study entry this sample may still be collected
 - If the baseline ctDNA sample is missed for any reason, please continue with the on treatment, end of treatment and follow up samples.
- Surgery site to ship diagnostic FFPE tissue to RNOH (coordinated by UCL CTC)
- Collect information about frozen tumour samples (where sample stored, reason sample not taken if applicable)

Patients receiving neoadjuvant chemotherapy

• Whole blood samples for CTCs, collected prior to the start of chemotherapy

Patients on PBMC substudy (UCLH site only)

Whole blood samples for PBMCs, collected prior to the start of neoadjuvant chemotherapy.

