10.5. Whole blood samples for ctDNA, methylation profiles and future research

Whole blood samples for future research including measurement of cell free DNA and analysis of methylation profiles may be collected from all patients who have consented to this. **These samples are optional.**

10.5.1. ctDNA Collection time points

Samples from all patients consenting to this should be collected at the following timepoints (at the same time that routine bloods are taken):

- Baseline (prior to start of neoadjuvant chemotherapy if applicable)
- During treatment:
 - For patients receiving **MAP** chemotherapy collect Pre cycle 2 day 21 methotrexate (ideally up to 3 to 7 days prior and 14 days post cycle 2) or pre surgery if this is not possible
 - For patients receiving **AP or other** chemotherapy, collect pre cycle 3 (ideally up to 3 to 7 days prior and 14 days post cycle 2) or pre surgery if this is not possible
- End of chemotherapy treatment (NOT end of mifamurtide treatment if applicable)
- At clinic visit during follow up no more than 6 monthly.
- At relapse (local recurrence or metastases)

10.5.2. ctDNA Processing and shipping

Whole blood should be collected into 2 x 10 mL BD Vacutainer® PAXgene ccfDNA blood collection tubes and inverted 10 times to mix. Samples must be shipped to RNOH on the day they are collected, using the shipping materials provided.

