7.	Determine feasibility of using standard pathology reporting to assess margin status for risk of local recurrence	 Collection rate of pathology reports in patients undergoing surgery Characterisation of tumour size, assessment of resection margins, % necrosis
Pa	tient Reported Outcome	
1.	Determine feasibility of data collection for validation of a sarcoma assessment measure (SAM) in patients undergoing treatment for OS	 Completion rate of SAM, TESS, EORTC-QLQ-C30 and GRC Descriptive analyses of PROs

17.2.2. Stage 2

17.2.2.1: Support and development of ICONIC infrastructure

The first aims for Stage 2 are:

- to support ongoing recruitment to the ICONIC study with additional follow up to form a cohort of a minimum of 300 patients with a median of approximately 56 months follow up
- to continue the collection of tissues and blood samples for CTC and plasma for circulating DNA (ctDNA)
- to collect peripheral blood mononuclear cells in a cohort of patients for IO research
- to establish an imaging biorepository for collaborative imaging biomarker studies.

Analysis of patient outcomes will be descriptive, using Kaplan-Meier methods for survival outcomes (e.g. overall survival, event-free survival and progression-free survival) and counts/frequencies for categorical outcomes (e.g. pathological response to chemotherapy).

Predictors of patient outcome will be assessed using standard regression techniques: Cox regression for survival outcomes, logistic regression for categorical. We will consider the following potential predictors of patient outcome:

- Blood biomarkers: serum biomics and ctDNA/CTCs
- Baseline characteristics (age, performance status, grade, primary site, tumour size, stage)
- Patterns of treatment
- Tissue biomarkers for IO research

Research questions	Planned analysis
Evaluate serum biomarkers (ALP, LDH) as prognostic markers in OS	Quantify serum biomarkers at baseline (pretreatment) and changes in response to chemotherapy.
	Characterise distribution of serum biomarkers as histograms and ranges (min, max, IQR, median)
	Assess serum biomarkers for prognostic value by using Cox regression (time-to-event outcomes) and logistic regression (categorical outcomes)
Evaluate ctDNA as predictors of response and outcome in OS	Quantify ctDNA biomarkers at baseline (pretreatment) and changes in response to chemotherapy.
	Characterise distribution of ctDNA as histograms and ranges (min, max, IQR, median)

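### Baseline serum markers and blood counts are timed from registration rather than from first treatment, yet are analysed as pre-treatment values

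*Protocol*

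**What the plan says.** **Collection.** Section 9.2.1 opens its list of baseline clinical data with "The following data should be collected from routine assessments carried out within 28 days of registration". The list includes haemoglobin, neutrophils, lymphocytes and platelets, and "Biochemistry: CRP, albumin, ALP, LDH, creatinine". The schedules in Appendix 2 give the window as 28 days after registration, which is narrower than 9.2.1. Neither place mentions the start of treatment.

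**Who can be registered, and when.** The only exclusion in section 6.2.2 is "Diagnosis more than four months prior to registration". Section 9.2.1 has an entry headed "Primary tumour: Surgery (if already performed", and section 9.2.4 says of the ctDNA sample: "NB if patient has started chemotherapy prior to study entry this sample may still be collected". The protocol therefore foresees patients whose treatment began before study entry.

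**Analysis.** For serum ALP and LDH, section 17.2.2.1 plans to "Quantify serum biomarkers at baseline (pretreatment) and changes in response to chemotherapy" and then to assess prognostic value by Cox and logistic regression. The power section takes 90% of 195 patients, giving 176 serum values split at the median into 88 per group.

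**Other baseline samples.** CTCs are tied to treatment: "Whole blood samples for CTCs, collected prior to the start of chemotherapy". PBMCs are to be drawn before neoadjuvant chemotherapy, and PROs before treatment if possible. For ctDNA, section 10.5.1 says "Baseline (prior to start of neoadjuvant chemotherapy if applicable".

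**The concern.** A blood result that obeys the collection rule need not meet the analysis definition. Two cases follow from the wording:

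- If treatment began before registration, no result inside the Appendix 2 window (after registration) is pre-treatment.
- If treatment began more than 28 days before registration, no result is pre-treatment even if 9.2.1 is read as allowing 28 days on either side.

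In both cases the true pre-treatment result is probably in the hospital record, but the protocol does not ask for it. Section 9.2.1 lists dates for imaging, biopsy and surgery but none for the bloods.

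The serum marker question is then exposed in three ways. A treated value may stand in for a pre-treatment one in the prognostic models. The change with chemotherapy may start from a value already altered by chemotherapy. And whether a value is usable depends on how quickly a site registers its patients.

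**Working it through.** **1. How late can a baseline value be?** Four months from diagnosis to registration (6.2.2) plus 28 days (9.2.1, Appendix 2) is about five months after diagnosis. This is the outer limit and needs both the latest registration and the latest draw.

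**2. Inputs for power (section 17.2.2.1).** Two-sided 5% level; 65% of 300 = 195 patients with both treatments; 90% of 195 = 175.5, stated as 176; 88 per group; overall response about 40%.

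**3. Reproducing the plan's figures.** With n per group, difference d = p2 − p1 and mean p̄,

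power = Φ{ [d − 1.96·√(2p̄(1−p̄)/n)] / √[(p1(1−p1) + p2(1−p2))/n] }.

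For 30% v 50% with n = 88: √(2·0.4·0.6/88) = 0.0739, times 1.96 = 0.1448; the denominator is √(0.46/88) = 0.0723; so Φ(0.0552/0.0723) = Φ(0.764) = 77.8%, as stated. The other serum rows come out at 99.99%, 98.64% and 52.87%, against 99.9%, 98.6% and 52.9% stated. The table is arithmetically right; it simply takes every baseline value as valid.

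**4. Allowing for late values.** Let f be the share of serum values drawn after treatment began. The documents do not give f, so 10% to 30% is an assumption.

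- *Kept, uninformative:* the observed difference becomes d(1−f) around 40%, with n = 88. At f = 20%, d = 0.16 (32% v 48%): (0.16 − 0.1448)/√(0.4672/88) = 0.209, power 58.3%.
- *Excluded:* d is unchanged and n = 88(1−f). At f = 20%, n = 70.4: (0.20 − 0.1618)/0.0808 = 0.472, power 68.2%.

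| f | 30% v 50%, kept | apparent risk ratio, kept | 30% v 50%, excluded | 25% v 55%, kept | 25% v 55%, excluded |
|---|---|---|---|---|---|
| 0 | 77.8% | 1.67 | 77.8% | 98.6% | 98.6% |
| 10% | 68.6% | 1.58 | 73.3% | 96.1% | 97.7% |
| 20% | 58.3% | 1.50 | 68.2% | 90.8% | 96.1% |
| 30% | 47.4% | 1.42 | 62.3% | 81.7% | 93.5% |

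**5. ctDNA set alongside.** The power section reports that in Stage 1 not every baseline ctDNA sample could be taken before treatment, and it assumes 150 of 300 patients with adequate pre-treatment samples. Section 10.5.1 and Appendix 2 (footnote J in the surgery-first schedule, footnote M in the neoadjuvant schedule) set a pre-treatment default with a fallback. The serum calculation has no such allowance and the serum rule no such default.

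**The case against.** The best defence is that section 17.2.2.1 confines the analysis to pre-treatment values, that chemotherapy and surgery dates are collected, and that choosing which record counts as baseline is ordinary SAP work. This is right as far as it goes: a reader might infer that the plan intends to analyse treated values as pre-treatment ones, and the protocol does not say so. But an SAP can only choose among the values collected. Where the pre-treatment result lies outside the window, it can use a treated value or lose the patient, so the gap sits in the collection rule.

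It can also be said that 9.2.1 is largely retrospective capture of the diagnostic work-up, and that its wording admits results from before registration. That helps patients registered promptly. It does not help those treated more than 28 days before registration, and Appendix 2 closes that reading.

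A reader might infer that ctDNA suffers equally, or that 9.2.4 contradicts 10.5.1. The documents do not support this. Section 9.2.4 only permits a late sample to be collected, without saying it will be analysed as pre-treatment; the samples also serve methylation profiling and future research; and the cohort has already been reduced to 150.

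Finally, the share of late values is unknown, and the larger power losses assume that late values are both kept and wholly uninformative. That stands, which is why both handling rules are shown.

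**Conclusion.** The mismatch is real for the routine serum markers and blood counts, and it does not depend on any assumed figure: the collection window is tied to registration, while the serum analysis presumes a value from before treatment.

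Its size is uncertain. At an assumed 10% to 30% of late values, power for 30% v 50% drops from 77.8% to between 68.6% and 47.4% if they are kept and uninformative, or to between 73.3% and 62.3% if excluded. For 25% v 55% it stays at 81.7% or above in either case. These figures concern pathological response only, and assume the late share is the same in both marker groups.

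A reader might infer that marker effects are bound to be diluted. That is not established: ALP or LDH measured on treatment may already reflect response and could push the association the other way. Nor does the point undermine the study as a whole. The primary objective is data and biospecimen collection, and the protocol describes the biomarker analyses as hypothesis generating. It should be fixed because it affects a named Stage 2 question and the remedy is cheap.

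**What to change.** - In section 9.2.1 and both Appendix 2 schedules, ask for the last result of each routine blood marker before the first anti-cancer treatment of any kind, with its date, even if it predates the 28-day window. Give the window the same wording in both places.
- In section 17.2.2.1, define baseline as a value dated before first treatment, and state how patients without one are handled.
- For ctDNA, keep collecting the late samples that 9.2.4 permits, but label them on-treatment and leave them out of the pre-treatment and change analyses.

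The cost is protocol and eCRF wording, plus retrieval of routine results from hospital records, including for patients already enrolled. No new blood draw is needed. Some late ctDNA samples would not count towards the pre-treatment analysis.
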